## 5. Data Handling

#### 5.1. Time Points and Visit Windows

#### 5.1.1. General Definitions

All assessment days will be related to the day of first dose of treatment.

Day 1 is defined as first dose of treatment. Relative days after Day 1 are calculated as (assessment date – Day 1 date) + 1. Relative days prior to Day 1 are calculated as (assessment date – Day 1 date). The day prior to Day 1 is Day -1. Day 0 is not defined.

The date of the first dose of treatment for each subject will be taken from the *Study Drug Administration (Oral)* eCRF page at Visit 3. If the date in this eCRF page is missing, alternatively the date of randomization + 1 will be used.

**The date of the last dose of treatment** for each subject will be taken from the *End of Treatment* eCRF page. If the date in this eCRF page is missing, alternatively the Completion or discontinuation date of *Disposition – End of Study* eCRF form will be used. If the date is missing because the subject was lost to follow-up, the date of the last visit will be imputed, if appropriate.

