3.2. End of Study Definition

In both Part A and Part B of this study, a subject is considered to have completed the study if he/she has completed the Week 16 visit.

The end of the study is defined as the date of the last visit of the last subject in the study.

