4.3.3. Temporary or Permanent Discontinuation of Study Treatment

In rare instances, it may be necessary for a subject to temporarily interrupt or permanently discontinue the study drug. If a subject requires temporary interruption of the study drug, the study team should consult with the study medical monitor and sponsor. In this study, every attempt will be made to prevent missing data and to obtain complete follow-up of all subjects for the study duration. Investigators will be trained to minimize full withdrawals wherever possible. Subjects who permanently discontinue the study drug are not required to withdraw from the study. These subjects will be encouraged to remain in the study and asked to conduct the remaining study visits as outlined in the protocol.

FINAL 10 AUG 2022 Page 41 of 73

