Appendix 4 - Schedule of Assessments

1. Schedule of Assessments for Part A

Visit	1	2	3	4	5	6	7	8	9	10
				(remote°)		(remote°)		(remote°)		(remote°)
Assessment ^a	Screening ^b (Day -15 to Day -2)	Day -1	Day 1	Day 3 (±1 day)	Day 15 (Week 2) (±2 days)	Day 17 (±1 day)	Day 29 (Week 4) (+3 days)	Day 57 (Week 8) (±5 days)	Day 85 or ET (Week 12) (±5 days)	Day 113 (Week 16) (-2/+5 days)
Informed consent	X									
Inclusion/exclusi on criteria	X									
Demographic data	X									
Medical history	X									
Serum pregnancy test ^c	X									
Urine pregnancy test ^c			X		X		X		X	
FSH d	X									
Vital signs e	X		X		X		X		X	
Physical examination ^f	X		X		X		X		X	
12-lead ECG g	X		X		X		X		X	
									1)	
Randomization		X								
Coagulation panel (aPTT, PT, INR)	X									
Laboratory safety tests ⁱ	X		X	X	X	X	X	X	X	
Study drug administration ^j			X	X	X	X	X	X	_	

FINAL 10 AUG 2022 Page 69 of 73

Visit	1	2	3	4	5	6	7	8	9	10
				(remote°)		(remote°)		(remote°)		(remote°)
Assessment ^a	Screening ^b (Day -15 to Day -2)	Day -1	Day 1	Day 3 (±1 day)	Day 15 (Week 2) (±2 days)	Day 17 (±1 day)	Day 29 (Week 4) (+3 days)	Day 57 (Week 8) (±5 days)	Day 85 or ET (Week 12) (±5 days)	Day 113 (Week 16) (-2/+5 days)
Drug accountability			X		X		X		X	
Dose escalation					X					
AE recording	X	X	X	X	X	X	X	X	X	X
Concomitant medications	X	X	X	X	X	X	X	X	X	X
Blood sample for drug assay (PK)			X ^k (pre-dose, 1 hr, 2 hr, 3 hr, 6 hr post dose)		X k (pre- dose, 1 hr, 2 hr, 3 hr, 6 hr post dose)		X ^k (pre-dose, 1 hr, 2 hr, 3 hr, 6 hr post dose)		Х	
Blood sample for cGMP assay (target engagement)		X k (0hr, 1 hr, 2 hr, 3 hr, 6 hr)	X k (pre-dose, 1 hr, 2 hr, 3 hr, 6 hr post dose)		X k (pre-dose, 1 hr, 2 hr, 3 hr, 6 hr post dose)		X ^k (pre-dose, 1 hr, 2 hr, 3 hr, 6 hr post dose)		X	
Spot urine sample for cGMP		Х	X		X		Х		X	
6 hr urine collection for cGMP		X	X		X		X			
Echocardiogram	X									_
Dispense study drug			X m		X ^m		X ^m			
Return study drug					X n		X n		X n	

[figure not shown]
CONFIDENTIAL

FINAL 10 AUG 2022 Page 70 of 73

[figure not shown]
Abbreviations: AE = adverse event; aPTT: activated partial thromboplastin time; cGMP = cyclic guanosine monophosphate; ECG = electrocardiogram; ET = end of trial; FSH = follicle-stimulating hormone; hr = hour; INR = international normalized ratio; PK = pharmacokinetics; PT = prothrombin time

- a. All assessments will be performed pre-dose unless otherwise specified.

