- b. All screening laboratory tests should ideally be performed on Day -15 to ensure eligibility assessment completed during screening window. In rare situations, if the laboratory reporting is delayed due to unforeseen circumstances (e.g., transit delays, lost sample, or outstanding queries), up to 21 days of screening will be accepted.
- c. Women of childbearing potential only.
- d. FSH will only be measured for women <55 years of age who have not had a menstrual period for ≥12 months at screening.
- e. Vital signs, including heart rate, blood pressure (systolic and diastolic), respiratory rate, and temperature, will be measured at the time-points specified in the above table and at all unscheduled visits as applicable. Vital sign measurements will be recorded with the subject in a seated position and after the subject has been resting for at least 5 minutes. All measurements will be performed singly. For any abnormal vital sign finding, further assessment should be performed as deemed necessary by the investigator. In case of re-screening, all vital sign parameters will be rechecked as described above.
- f. Physical examination will include assessment of heart, lung, extremities, body weight, and height. Height will only be assessed at screening. Body weight will be assessed at screening and at Visit 9. All the other assessments will be performed at all the applicable time-points and at all unscheduled visits as applicable.
- g. Resting 12-lead ECGs will be recorded at the time-points specified in the above table and at all unscheduled visits as applicable. Resting 12-lead ECGs will be recorded after the subject has been supine and at rest for at least 5 minutes.
- h. The blood sample will be collected 12-24 hours after last dose of study drug.
- i. Laboratory safety tests will include biochemistry, urinalysis, and hematology. Please refer to Appendix 2 for the specific analytes of each test. Laboratory safety tests will be performed at the time-points specified in the above table and at all unscheduled visits as applicable. All laboratory safety tests will be analyzed at a central laboratory.
- j. On the days of Visit 5 and Visit 7, subjects will be instructed NOT to take their dose of study drug before the pre-dose blood and urine sampling. Subjects will not take the study drug at Visit 9. They will be instructed to take the study drug through the day before Visit 9.

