#### **6.5.** Measurements of Treatment Compliance

Treatment compliance is defined as the number of tablets that were actually taken relative to the number of tablets that should have been taken as per the protocol for the duration of actual treatment exposure.

In general, the percentage compliance, assessed by tablet count, will be calculated as follows:

Compliance (%) =  $\frac{Number\ of\ tablets\ dispensed-Number\ of\ tablets\ returned}{Number\ of\ days\ on\ treatment\ x\ 2\ x\ Number\ of\ tablets/dose} \times 100\%$ 

Number of tablets per dose is mg dosing.

Number of days on treatment will be calculated as follows:

(last dose date of treatment - first dose date of treatment) + 1

The calculated percentage compliance will be categorized as:

CONFIDENTIAL

- < 80% compliance
- $\geq$  80% to  $\leq$  125% compliance
- > 125% compliance

Compliance will be summarized for the SAF by treatment group and overall for Part A of the study as follows:

- Percent compliance will be presented by default summary statistics.
- Number and percentage of subjects within each of the compliance categories will be presented. Any subjects with missing data will be presented as part of a "Missing" category.

In addition, for part A, compliance by period (period 1, period 2, period 3 and pooled periods 2 and 3) will be calculated using the same formula with the denominator (number of days on treatment) corresponding to the number of days within each period. Compliance by period will be summarized in the same way as overall compliance.

Treatment compliance will be listed together with exposure for the SAF. Missing data will not be imputed and only original data for those fields (for example, date fields) will be presented in the listing together with derived variables such as the calculated compliance (%) and exposure duration.

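### A missing last-dose date is replaced by the End of Study date, which for a completer falls about 29 days after planned dosing ended and overstates that subject's exposure and at-risk time

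*SAP*

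**What the plan says.** SAP 5.1.1 sets the source of the last-dose date (the End of Treatment page) and two fallbacks. The general one is: "If the date in this eCRF page is missing, alternatively the Completion or discontinuation date of" the End of Study disposition form. The only exception is: "If the date is missing because the subject was lost to follow-up, the date of the last visit will be imputed, if appropriate".

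The protocol separates the end of dosing from the end of the study:

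- Protocol 3.2: "a subject is considered to have completed the study if he/she has completed the Week 16 visit". Appendix 4 places that visit at "Day 113 (Week 16) (-2/+5 days").
- Appendix 4, footnote j, on Visit 9: "They will be instructed to take the study drug through the day before Visit 9". Visit 9 is at "Day 85 or ET (Week 12) (±5 days").
- Protocol 4.3.3: "Subjects who permanently discontinue the study drug are not required to withdraw from the study". They are encouraged to attend the remaining visits.

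The last-dose date is used in several places in the SAP:

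- the end of the Treatment Period and of Period 3, and of Period 1 or 2 for early stoppers (5.1.4);
- imputed stop dates for adverse events and medications (5.2.3);
- days on treatment in the compliance denominator, "last dose date of treatment - first dose date of treatment) + 1" (6.5);
- weeks of exposure (6.7.1);
- at-risk time in the exposure-adjusted AE and SAE rates, which are the primary safety analysis (6.7.2).

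Neither document caps the substituted date at Visit 9 or at the last documented dose.

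**The concern.** The substitute answers a different question. The End of Study date records when the subject left the trial, not when the subject stopped taking tablets. For a completer, the protocol puts a planned off-drug follow-up of about four weeks between the two. The fallback counts that follow-up as treatment in Period 3.

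Three outputs are at stake for an affected subject. Exposure is overstated and may change category. Compliance is understated, because the denominator grows and the tablet count does not. Off-drug days join the at-risk time for Period 3 and for pooled Periods 2 and 3, and events from follow-up can be assigned to Period 3. The subject who stops drug early and stays on, a case the protocol foresees, is affected most.

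**Working it through.** **Inputs.** Day 1 is the first dose (SAP 5.1.1). Period 2 starts on Day 15 and Period 3 on Day 29 (SAP 2.1). Visit 9 is Day 85, window Days 80 to 90, and Week 16 is Day 113, window Days 111 to 118 (Protocol Appendix 4). Planned last dose is the day before Visit 9: 85 − 1 = Day 84. Part A has about 60 subjects randomized 2:1, so 40 on CRD-740 and 20 on placebo.

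**The plan's own figure.** Days 1 to 84 are 84 days; 84/7 = 12.0 weeks, the treatment duration stated in SAP 2.1. Day 84 is therefore the right reference.

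**Size of the gap.** Nominal: 113 − 84 = 29 days. Shortest: Visit 9 on Day 90 and Week 16 on Day 111, 111 − 89 = 22. Longest: Visit 9 on Day 80 and Week 16 on Day 118, 118 − 79 = 39.

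**Nominal completer, SAP formulas**

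| Quantity | Last dose Day 84 | Fallback Day 113 |
|---|---|---|
| Exposure, (last − first)/7 | 83/7 = 11.86 weeks | 112/7 = 16.0 weeks |
| Days on treatment, last − first + 1 | 84 | 113 |
| Compliance if every dose was taken | 168/168 = 100% | 168/226 = 74.3% |
| Period 3 length, from Day 29 | 56 days | 85 days |
| Period 3 compliance | 100% | 56/85 = 65.9% |
| Pooled Periods 2 and 3, from Day 15 | 70 days | 99 days (99/70 = 1.41) |

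The 168 and 226 are doses at two per day. The 74.3% assumes the same number of tablets per dose throughout; that number is redacted in SAP 6.5. It cancels within Period 3, so 65.9% does not need the assumption. Across the visit windows, overall compliance runs from 79/118 = 66.9% to 89/111 = 80.2%.

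**Early stopper who attends Week 16.** Last dose Day 20, recorded as Day 113: 113 − 20 = 93 days too long. Pooled Periods 2 and 3 time is 99 days instead of 6 (Days 15 to 20). SAP 5.1.4 leaves open whether the extra days go to an overlong Period 2 or to a Period 3 that never happened; the pooled figure is the same.

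**Arm level.** If all planned subjects complete without the event in question, Periods 2 and 3 time is 40 × 70 = 2,800 days on CRD-740 and 20 × 70 = 1,400 on placebo. One affected completer adds 29/2,800 = 1.0% or 29/1,400 = 2.1%.

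**The case against.** The best case for leaving the rule alone is that it may hardly operate. It applies only when the End of Treatment date is missing, and nothing in the documents suggests this will be common. SAP 6.2 identifies treatment discontinuers by a reason entered on the same form, so a known discontinuer has at least part of it completed. Subjects lost to follow-up have their own rule. For those who leave the study when they stop drug, the End of Study date is close to the last dose. No between-group comparison of AEs is planned (SAP 6.7.2), and the primary efficacy analysis of Week 4 cGMP does not use the last-dose date. All of this stands, and it limits the reach of the point.

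Other limits also stand. That the End of Study date equals the Week 16 visit date is inferred from Protocol 3.2; SAP 6.2 defines completion by a yes/no item, and the form itself is not in the documents. Landing in the over-12-weeks exposure category is not in itself a sign of error, because Visit 9 on Days 87 to 90 puts a completer there legitimately. SAP 6.5 says missing data are not imputed in the compliance and exposure listing. That should make the missing date visible there, but the text does not withdraw the 5.1.1 substitution from the derived values or the summaries.

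Four stronger readings are tempting, and the documents do not support them:

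- *That the rule always lengthens exposure.* It does so materially only when off-drug follow-up comes between last dose and End of Study.
- *That missing dates will cluster in irregular discontinuers.* This is plausible, but no text bears on it.
- *That safety rates shift by 41%.* That is one subject's time, not an arm's rate.
- *That rates must fall.* Follow-up events can enter the numerator along with the extra days, so the direction is not fixed.

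**Conclusion.** The point holds as a derivation error in a stated rule, conditional on a missing End of Treatment date. For a nominal completer the substitute is about 29 days late, and for an early stopper who stays in the study it can be months late. The subject-level distortion is large. The arm-level effect is small, about 1% or 2% of Periods 2 and 3 time per affected completer, and would matter only if several dates were missing or the affected subjects had stopped early.

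This rests on three assumptions: that the End of Study date for a completer is the Week 16 visit; that visits fall on the nominal schedule, or within the windows for the ranges; and, for overall compliance only, that tablets per dose is constant. The number of missing dates is unknown. The rule should be corrected because it feeds the primary safety rates and is cheap to change, but it does not threaten the trial's main conclusions.

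**What to change.** In SAP 5.1.1, remove the End of Study date as an uncapped substitute and replace it with the following:

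1. Query the missing date with the site before database lock.
2. If it is still missing, use the first available source in this order:
   - a last-dose date documented in dosing or drug accountability and return records;
   - a documented treatment-stop date, such as one linked to an AE whose recorded action was withdrawal of drug, but not an AE onset date alone;
   - otherwise, the earlier of the End of Study date and the day before Visit 9/ET.
3. Cap every substitute at the day before Visit 9/ET, and say which day serves as the cap if Visit 9 was missed.
4. Flag imputed last-dose dates in the exposure listing.

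The order must be ranked. Taking the earliest of the available dates would introduce the opposite error, because Appendix 4 marks study drug administration only through Visit 8 (Day 57), so a completer's last scheduled record could cut exposure short.

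The cost is a few lines of SAP text and a little extra derivation work. One weakness remains: an early stopper with no dosing record and no documented stop date may still be overstated, up to the cap. For the Day 20 example that would be 84 − 20 = 64 days instead of 93.

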### 5.1.2. Baseline Value and Change from Baseline

Baseline values for the primary efficacy variable in Part A (plasma cGMP) are the plasma cGMP values collected on Day -1 (at 0hr, 1hr, 2hr, 3hr, and 6hr) time-matched to Day 29 values. An  $AUC_{0-6h}$  will also be derived from those values.  $AUC_{0-6h}$  derivation is described in Section 6.6.1. In addition, baseline value for 6-hour urine collection will be the value collected on Day -1.

For all other variables, independently from study Part, **baseline value** is defined as the last non-missing value collected before the first dose of treatment. If assessment is performed on Day 1, it will be considered performed before the first dose intake unless the date/time of assessment confirms that it was performed after the first dose intake.

Change from baseline at Week X will be defined as Week X value – Baseline value.

Change from Week X to Week Y will be defined as Week Y value – Week X value.

CONFIDENTIAL

## 5.1.3. Screening Period

For all subjects, the screening period is defined as the period from informed consent to the first dose of treatment. For some variables, data from more than one assessment within the screening period can be collected prior to the first dose of treatment.

#### 5.1.4. Treatment Period

Data collected at Day 1 will be assigned to the Treatment Period unless the time (HH:MM) of data collection and time (HH:MM) of first dose of treatment are both recorded and the data collection time is before the time of first dose of treatment. In this case, the assessment will be assigned to the screening period. If the time (HH:MM) of data collection is not recorded but the protocol and / or eCRF includes an instruction to the effect that all Day 1 assessments are to be performed prior to the first dose of treatment, the data collected at Day 1 will be assigned to the screening period. However, adverse events and medications starting on Day 1, will be assigned to the Treatment Period.

The Treatment Period is defined as the period from the date / time of the first dose of treatment up to and including the date / time of the last dose of treatment.

Treatment period in Part A comprises 3 dosing periods:

Period 1 (dose of ) from date of the first dose of treatment at level till date of the first dose of treatment at level;

Period 2 (dose of ) from date of the first dose of treatment at level till day before Visit 7;

Period 3 (dose of ) from the dose of treatment on Visit 7 till the date of the last dose of treatment.

If subject discontinues during Period 1 or Period 2, the date of the last dose of treatment will be considered as end of the respective period.

#### 5.1.5. Visit Windows

Table 4 Definition of Visit Windows for Efficacy and Safety Assessments provides the relative trial day ranges to be applied to the assessment / sample collection date to derive the analysis visits for analyses of trial assessments.

The following considerations are to be followed when deriving the analysis visit:

- The relative day number of the assessment lies between the lower and upper boundary of the analysis visit window (the boundary values are included)
- Both scheduled and unscheduled assessments are included for visit windowing
- If there are two or more valid assessments for a defined window the following rules will be applied:

CONFIDENTIAL

- CONFIDENTIAL
  Protocol Reference: CRD-740-201
- If there are multiple assessments with non-missing assessment results for any specified analysis visit window, the assessment that is closest to the target day of analysis window will be used for analysis
- If there are two or more assessments with non-missing results and the same distance to the planned study day, the assessment prior to the planned study day will be used for analysis.

Table 4 Definition of Visit Windows for Efficacy and Safety Assessments Part A

Visit	Target Day of Visit a	Protocol Visit Windows	Analysis Visit Window	Target Day of Analysis Visit	Analysis Visit
Screening (Day -15 to Day -2)	Day -15	Day -15 to Day -2	Day -21 to Day -2	Day -15	Screening
Visit 2, Day -1	Day -1	Day -1			Day -1
Visit 3, Day 1	Day 1	Day 1	Day 1	Day 1	Baseline*
Visit 4, Day 3 (remote)	Day 3	Day ± 1	NA		
Visit 5, Day 15	Day 15	Day ± 2	Day 2 to Day 24	Day 15	Week 2
Visit 6, Day 17 (remote)	Day 17	Day ± 1	NA		
Visit 7, Day 29	Day 29	Day ± 3	Day 25 to Day 43	Day 29	Week 4
Visit 8, Day 57 (remote)	Day 57	Day ± 5	NA		
Visit 9, Day 85	Day 85	Day ± 5	Day 71 to Day 99	Day 85	Week 12
Visit 10, Day 113 (remote)	Day 113	Day – 2/ + 5	NA		

<sup>a Relative to first dose of treatment

NA= Not Applicable

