### 6.6. Efficacy Analysis

Efficacy assessments will undergo visit windowing procedure as described in Section 5.1.5 and will be analyzed using analysis visits.

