#### 6.6.2. Sensitivity Analysis for the Primary Efficacy Endpoints

#### Part A

The following sensitivity analyses of the primary efficacy endpoint will be performed:

- Primary analysis will be repeated on the PP population.
- Primary analysis will be repeated on the Week 2 Analysis population. This analysis will be performed for interim DMC purposes only.
- Primary analysis will be repeated on the Week 4 Analysis population. This analysis will be performed for interim DMC purposes only.
- Change from baseline in log-transformed plasma cGMP AUC over time will be analyzed in the mITT population using a mixed model for repeated measures (MMRM) including treatment, post-baseline visit (Visits 3, 5 and 7), Entresto use, treatment-by-visit interaction, treatment-by-Entresto interaction, visit-by-Entresto use interaction, and baseline EF as a covariate with random effects for subject, intercept, and slope. The covariance structure will be unstructured. No imputation of missing data will be performed. The least-square means of log (plasma cGMP AUC) and associated two-sided 95% CI for each treatment, the estimated least square mean treatment differences (on the log scale), and corresponding two-sided 95% CI coming from the MMRM will be given for all visits.
- The MMRM analysis described above will be conducted on raw plasma cGMP AUC in the mITT population.

CONFIDENTIAL

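### Week 4 cGMP is assigned by calendar day and not by dosing visit, so a very late Visit 5 profile can become the primary endpoint value in place of Visit 7

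*SAP*

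**What the plan says.** SAP 6.6 opens with a rule for all efficacy analyses: "Efficacy assessments will undergo visit windowing procedure as described in Section 5.1.5 and will be analyzed using analysis visits". SAP 5.1.1 sets the clock: "All assessment days will be related to the day of first dose of treatment". In SAP Table 4 the Week 2 window is Day 2 to Day 24 with target Day 15. The Week 4 window is "Day 25 to Day 43" with target Day 29.

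SAP 5.1.5 then says how one result is chosen. "Both scheduled and unscheduled assessments are included for visit windowing". When several results share a window, "the assessment that is closest to the target day of analysis window will be used for analysis". When two are equally far from the target, "the assessment prior to the planned study day will be used for analysis". Nominal visit, dosing period and time since escalation are not conditions. SAP 6.6.1 derives AUC0-6 at each profile visit and analyses the change at Week 4, but does not tie Week 4 to Visit 7.

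Protocol Appendix 4 puts Visit 5 at Day 15 ± 2 days, marks dose escalation there, and schedules a full cGMP profile at both Visit 5 and Visit 7. It heads the Visit 7 column "Day 29 (Week 4) (+3 days", whereas the protocol-window column of SAP Table 4 gives ±3 days. The MMRM in SAP 6.6.2 describes its time factor as "post-baseline visit (Visits 3, 5 and 7".

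**The concern.** In Part A the dosing history follows the visit and not the calendar. SAP 5.1.4 recognises this: Period 2 runs from the first dose at its level to the day before Visit 7, and Period 3 starts with the dose at Visit 7. The protocol gives Period 2 a length of two weeks, so the Week 4 profile is meant to be taken after about two weeks of Period 2.

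The windowing rule ignores this anchor. A Visit 5 profile taken late enough is eligible for Week 4 and can be chosen over Visit 7. Subjects hold their dose at Visit 5 until the pre-dose sample is drawn (Appendix 4, footnote j). The 0-hour value of that profile therefore reflects Period 1, and the later samples follow the first Period 2 dose. That last step is an inference from the schedule, because the dose levels are blacked out. At stake is which profile enters the only primary efficacy analysis of a trial of about 60 subjects.

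**Working it through.** The documents give no power, effect size or late-visit rate, so there is no planned figure to reproduce. The check applies the SAP 5.1.5 rule to Visit 5 and Visit 7 days.

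**Inputs.** Week 2 window Day 2–24 and Week 4 window Day 25–43, target Day 29, ties to the earlier day (SAP 5.1.5). Visit 5 on Day 13–17 (Appendix 4). Visit 7 on Day 29–32 (Appendix 4) or Day 26–32 (SAP Table 4). Period 2 of 14 days (protocol synopsis; SAP 2.1).

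**Rule.** Among profiles on Day 25–43, choose the smallest |day − 29|.

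**1. Visits inside protocol windows.** Visit 5 on Day 13–17 is below Day 25, so it is never a Week 4 candidate. Visit 7 is selected for every pair, whichever Visit 7 window is used. Days since the first Period 2 dose at Visit 7, by Appendix 4, run from 29 − 17 = 12 to 32 − 13 = 19.

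**2. Visit 5 late, Visit 7 held 14 days after it (assumed).**

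| Visit 5 | Visit 7 | Visit 5 distance | Visit 7 distance | Week 4 value |
|---|---|---|---|---|
| Day 18–24 | Day 32–38 | not a candidate | 3–9 | Visit 7 |
| Day 25 | Day 39 | 4 | 10 | Visit 5 |
| Day 29 | Day 43 | 0 | 14 | Visit 5 |
| Day 30 | Day 44 | 1 | outside window | Visit 5 |
| Day 43 | Day 57 | 14 | outside window | Visit 5 |

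The days between follow the same pattern. Table 4 has no analysis window between Day 43 and Day 71, so a Visit 7 profile on Day 44–57 is assigned to nothing. In all these substitutions the time since the first Period 2 dose is 0 days. The subject also has no Visit 5 profile in the Week 2 window.

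**3. Visit 5 late, Visit 7 kept at Day 29–32.** Visit 5 on Day 25 loses: its distance is 4, against 0–3. It would win only if Visit 7 were on Day 33 or later (Day 33 is a tie at 4). Visit 5 on Day 26–31 wins for some pairs, such as Day 26 with Day 32 (tie at 3) or Day 27 with Day 31 (tie at 2). In those pairs the visits are at most 32 − 26 = 6 days apart.

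**4. Size of the trigger.** Visit 5 must be at least 25 − 15 = 10 days after its target and 25 − 17 = 8 days beyond its protocol window.

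**5. Is the direction of bias known?** Assume 60 × 2/3 = 40 CRD-740 subjects, k of them substituted, and a Visit 5 effect equal to r times the two-week effect. The mean effect is multiplied by 1 − (k/40)(1 − r). The values of k and r below are assumptions, not document figures.

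- k = 1: 1 − 0.025 × 0.5 = 0.9875 at r = 0.5; 1 + 0.025 × 0.25 = 1.00625 at r = 1.25.
- k = 4: 1 − 0.1 × 0.5 = 0.95 at r = 0.5; 1 + 0.1 × 0.25 = 1.025 at r = 1.25.

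The sign depends on r, which the documents do not give.

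**The case against.** The strongest reply is that the trigger is remote. The Week 2 window already runs to Day 24, past the midpoint of the two targets, (15 + 29)/2 = Day 22, so a Visit 5 up to 9 days late is still Week 2. The protocol anchors Visit 7 to Day 29 and nowhere says that it moves when Visit 5 is late. Protocol 4.3.3 allows study drug to be interrupted but does not say that visits are delayed. The primary analysis is repeated on the Per Protocol Population, whose exclusion criteria sit in a separate spreadsheet and may cover such a deviation.

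The point on rarity stands, and so does the observation that the clearest cases need Visit 7 to move as well. But a shifted Visit 7 is what a two-week Period 2 would call for, and the mITT population, which carries the primary analysis, keeps subjects with late visits. A Per Protocol repeat does not change which profile the primary analysis uses.

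Three stronger readings are tempting, and the documents do not support them.

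- **The ANCOVA and the MMRM use different profiles.** A reader might infer this from the MMRM's list of visits. The windowing sentence in SAP 6.6 also governs 6.6.2, and the list may only label Table 4 rows. The wording is open; a conflict is not shown.
- **PK profiles are misassigned too.** The windowing sentence sits in the efficacy section and Table 4 is titled for efficacy and safety. SAP 6.8 summarises PK by visiting day.
- **The ±3 against +3 mismatch affects the endpoint.** Selection uses the analysis-window column, so the mismatch changes no selected value.

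**Conclusion.** The point holds as a statement of what the rule permits. With Visit 7 held 14 days after Visit 5, any Visit 5 on Day 25 to 43 supplies the Week 4 value, and the Visit 7 profile is passed over or falls in no window. The Week 4 value then comes from the start of Period 2. With visits on schedule this does not occur. It needs Visit 5 at least 8 days beyond its window, and few subjects, if any, should be affected.

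A reader might infer that each such subject dilutes the treatment difference by 1/40 = 2.5%. That would require the subject to show no drug effect at all, although he or she has been assigned CRD-740 throughout Period 1 and the later samples follow a Period 2 dose. With doses blacked out and no cGMP time course given, neither size nor direction can be derived. The case for acting is that the rule can contradict the SAP's own dosing periods and is very cheap to repair before unblinding.

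**What to change.** In SAP 5.1.5 and 6.6.1, define Week 2 and Week 4 plasma cGMP AUC0-6, and the 6-hour urine cGMP, as the nominal Visit 5 and Visit 7 collections, so that a Visit 5 profile can never serve as Week 4. State in 6.6.2 that the MMRM uses the same assignment as the ANCOVA. List Visit 7 profiles outside the protocol window with the days since the first Period 2 dose. Leave the calendar windows in place for other assessments.

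Separately, reconcile the Visit 7 protocol window between SAP Table 4 and protocol Appendix 4.

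The cost is SAP wording and one derivation rule. No new data are needed, and subjects seen on schedule keep the same value. The small downside is that a late Visit 7 stays in as Week 4 with no upper day limit. Keeping the calendar-window analysis as a sensitivity analysis addresses that.
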